The present study builds upon the momentum, resources, and research infrastructure of our pilot work to test the larger-scale and sustained impact of an addiction-based weight loss mHealth intervention with personalized coaching. Specifically, the proposed multi-site randomized controlled trial (RCT) tests will test the efficacy of an interactive addiction model based mobile health (mHealth) weight-loss intervention with personalized phone-coaching (AppCoach) compared to 1) interactive addiction model based mHealth weightloss intervention alone (App) or 2) Multidisciplinary in-clinic weight management program (Clinic).

The RCT will include youth regardless of their underlying co-morbidities because the targeted behaviors and weight management strategies are relevant and beneficial for all overweight and obese adolescents. Not only does this delivery modality remove many barriers (e.g., transportation, missed school days) that impact access and attrition in conventional, outpatient obesity interventions, but it strategically addresses underlying addictive eating behaviors to better support habit-formation in youth in their day-to-day environment. Assessment of the intervention's effect on zBMI, %BMI_{p95}, fasting metabolic parameters, addictive eating habits, executive function, and motivation for change will be obtained at enrollment, 3, 6, 12 and 18 months (1 year post intervention follow up). Another key aim of the study is to conduct a real-life economic analysis (costs, cost-savings and non-monetary benefits) of delivering the app with personalized phone- coaching compared to multidisciplinary weight-management. We will further explore whether primary and secondary outcomes differ by race and whether race moderates the relationship between initial intervention efficacy and prolonged weight maintenance.

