- a. Fasting lab results at enrollment are needed to determine baseline values. Participants that were referred to a weight management clinic at any of the participating sites may have had these labs drawn as part of their routine care. These results will be abstracted from the medical record if they are within 8 weeks of consent date. However, a research blood draw will be done at enrollment if these labs were not done as part of the participant's routine care. If the consent visit takes place virtually/by mail, the participant will be expected to travel to CHLA for a baseline research blood draw.
- b. All arms will have a follow up research blood draw at months 6 and 18.
- c. Each research blood draw will collect approximately 5 mL (1 teaspoon) of blood via venipuncture that will be used for the following testing: HbA1c, Total Chol, LDL, HDL, TG, AST/ALT, Glucose and insulin.

6. All participants

*Visit 1: if consenting via mail, these procedures will be completed at the 2nd session as visit 1 will be split in 2

** Each participant will have the opportunity to earn up to \$200 in gift cards for participation in this study: up to \$50 for participation in the intervention at 3 and 6 months and \$50 for going to the last 2 study visits (at 12 and 18 months). The amount of payment will be based upon how much of the intervention the participant completes.

***Visit 2 and 3 must occur within a 4-week period (+/- 2 weeks from the 3- or 6-month date) and Visits 4 and 5 must occur within an 8-week period (+/- 4 weeks from the 12- or 18-month date).

Study Visit Schedule for Group 3 (In-Clinic) (total visits = 9)

*Visit 1: if consenting via mail, these procedures will be completed at the 2nd session as visit 1 will be split in 2

The youth participants in this group will also earn up to \$50 at 3 months (visits 4) and 6 months (visit 7) for participation in the 6-month intervention and \$50 for completion of study visits 8 and 9.

The table below depicts the assessment time points and key measures.

Month	0	3	6	12	18
Covariates					
Co-Morbidities, race/ethnicity, household composition, socioeconomic status, and previous weight loss programs completed	x				
Primary Outcomes (Aim 1)					
Height, Weight, zBMI, %BMIp95	x	x	x	x	x
Secondary Outcomes / Mediators (Aims 2, 3)					
Youth Surveyed: Yale Food Addiction Scale-Children	x	x	x	x	x
CES-D	x	x	x	x	x
Perceived Stress Score	x	x	x	x	x
BRIEF 2	x				
ASRI	x	x	x	x	x
Food Craving Questionnaire	x	x	x	x	x

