Binge-Eating Disorder Screener	x		x	x	x
Satisfactory Survey			x		x
Physical Activity Questionnaire	x	x	x	x	x
SF-12	x	x	x	x	x
EQ5D	x	x	x	x	x
S-Weight	x		x		
Parent Surveyed:					
Demographic (Including Fast Food Consumption)	x				x
Height, Weight BMI	x	x	x	x	x
Health Encounters	x	x	x	x	x
Satisfactory Survey			x		x
Fasting Lab Tests: HbA1c, Total Chol, LDL, HDL, TG, AST/ALT, Glucose, Insulin	x		x		x

Post Study Follow-up Options:

1. After completion of the 6-month interventions participants will be offered the following choices for continued care:
 - a. Participants in groups 1 and 2 will have access to use the mobile app without coaching upon completion of the 6-month intervention. However, a participant owned iPhone is required in order to use the mobile app. Group 3 will have access to use the mobile app without coaching upon

completion of the study (post 18 month). Participants will have to own an iPhone in order to use the mobile app as it is an IOS App only.

2. All participants will receive a call from a study team member monthly for the 18-month study period.
 - a. They will discuss weight trends since the intervention completion and any interim health encounters (ED visits, hospitalizations, PMD visits, changes to medical history).
 - b. They will also discuss if any interim weight management strategies have been utilized or started.
3. All Participants will have an in person/virtual follow up 12 months and 18 months post consent (baseline) where a repeat weigh in and survey completion will occur. All participants will also have a fasting research blood draw at 6 and 18 months.

Enrollment and Retention:

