The primary outcome will be change in zBMI and excess BMI percent over the 95th percentile (%BMI_{p95}) compared to baseline, assessed at 3, 6, 12 and 18 months, both within the groups and compared between groups and in clinic group. For analysis over time, the Δ%BMI_{p95} (BMI percentile – 95th percentile), which is the distance (in kg/m²) from the 95th percentile, will be utilized³¹.

Secondary outcomes will include: compliance with App intervention, retention rates with scheduled phone calls and clinic visits, ASRI, BRIEF, Satisfaction survey, YFAS-c, fasting lab testing compared pre and post intervention. Collected lab studies will include: HbA1c, Lipid Panel, AST/ALT. Each of these lab tests are currently recommended for routine clinical care screening every 6-12 months in obese adolescents³.

An estimated cost analysis will be completed to determine the cost per patient to implement the 6 month AppCoach intervention, App alone intervention and multi-disciplinary in-clinic intervention (Clinic)³². Cost Analysis to include: time or expenses saved compared to in-clinic (travel, missed work or school); efficiency of clinic and staffing needs, including appointment duration and physical space requirements, and health care utilization rates and costs of care^{33, 34}.

Analytic Plan:

Power and Sample Size Estimates:

The power analysis is prepared for comparing (1) the difference in the mean change of zBMI and %BMIp95 between baseline, 6 months, and 18 months across App+Coach, App, and Clinic, (2) the difference in zBMI and %BMIp95 mean change between App+Coach and Clinic, and (3) the difference in zBMI and %BMIp95 mean change between App+Coach and App. Review of the literature revealed that the majority of studies utilize the change in zBMI to evaluate the effectiveness of weight management interventions in adolescents. However, Freedman et al. and the CDC have proposed utilizing alternative metrics for weight change such as %BMIp95 which may be more strongly associated with change in body size in adolescents. Therefore, both metrics were considered in the power calculation to further explore their use as outcome measures in youth with obesity and severe obesity.

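### The fasting-lab outcome is stated as a before/after comparison with no between-arm contrast, model or time point, and the lab list and lab times differ between sections

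*Combined protocol and SAP*

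**What the plan says.** **Outcomes.** The primary outcome is to be examined "both within the groups and compared between groups and in clinic group". The next paragraph lists the secondary outcomes, and there the labs appear as "fasting lab testing compared pre and post intervention". It continues: "Collected lab studies will include: HbA1c, Lipid Panel, AST/ALT".

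**Research Blood Draws (all arms).** After a baseline value, "All arms will have a follow up research blood draw at months 6 and 18". The panel is "HbA1c, Total Chol, LDL, HDL, TG, AST/ALT, Glucose and insulin".

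**Assessment table (before Post Study Follow-up Options).** The row "Fasting Lab Tests: HbA1c, Total Chol, LDL, HDL, TG, AST/ALT, Glucose, Insulin" sits under the heading that begins "Secondary Outcomes / Mediators (Aims 2, 3" and is marked at months 0, 6 and 18. The outcome schedule under Initial Visit marks fasting labs at the same three times, as a secondary outcome.

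**Introduction, description of the present trial.** The plan promises "Assessment of the intervention's effect on zBMI, %BMI_{p95}, fasting metabolic parameters" and other measures at enrolment and months 3, 6, 12 and 18. It describes month 18 as follow-up one year after the intervention.

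**Statistical Analysis.** The only change-from-baseline test is an ANOVA of %BMIp95 at week 24, and the mixed models also concern %BMIp95. One sentence covers all outcomes, but it only defines per-protocol sets.

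**The concern.** Randomisation lets the trial attribute a difference between arms to the intervention. A before/after change in one arm does not have that property. Participants are 14 to 18 years old, so metabolic markers can move with growth and puberty over 6 or 18 months. All arms also receive monthly calls, and those with comorbidities continue their usual subspecialty care. The plan itself separates participants who finished before mid-March 2020 from those who finished later, which acknowledges that calendar time may matter. Each of these can shift a marker in every arm whatever the intervention does.

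Two things are at stake. First, three separate before/after results invite the reading that a marker improved significantly in AppCoach but not in Clinic, which is not a test of the difference between them. Second, with no contrast and no time point fixed, both can be chosen after the data are seen. The trial takes fasting blood from adolescents in every arm, and no metabolic marker has a stated arm comparison.

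**Working it through.** The plan gives no effect size, standard deviation or power for any lab, so there is no planned figure to reproduce. The check is mainly textual.

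**1. Is an arm contrast for labs stated anywhere?** No.
- Outcomes gives one only for the primary outcome.
- Power and Sample Size Estimates covers zBMI and %BMIp95 only.
- Statistical Analysis tests %BMIp95 only.
- The one comparison that covers secondary outcomes as a class is the exploratory one by race, in the introduction.

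**2. Which time is post?** The intervention lasts 6 months, so month 6 is the natural reading. But the introduction also describes month 18 as post-intervention, and labs are scheduled at both times. The text allows month 6, month 18 or both.

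**3. Do the lab lists agree?** No.

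| Place | Markers |
|---|---|
| Outcomes | HbA1c, lipid panel, AST, ALT |
| Research Blood Draws; assessment table | HbA1c, total cholesterol, LDL, HDL, TG, AST, ALT, glucose, insulin |

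Taking the lipid panel as the four lipids, the lists have 1 + 4 + 2 = 7 and 9 markers. Glucose and insulin make the difference.

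**4. Do the lab times agree?** The two schedules and Research Blood Draws agree on months 0, 6 and 18. The introduction's 0, 3, 6, 12 and 18 includes two times without a draw.

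**5. Size of the remedy.** 9 markers × 2 times (months 6 and 18) × 2 contrasts (AppCoach vs Clinic, AppCoach vs App) = 36. At the plan's two-sided 0.05, the expected number of nominally significant results with no true effects is 36 × 0.05 = 1.8. This expectation does not require the markers to be independent.

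**6. Illustration only.** Suppose AppCoach and Clinic have the same true change, the arms are independent, and each before/after test has power p. The chance of a significant result in AppCoach but not in Clinic is p(1 − p): 0.5 × 0.5 = 0.25 at p = 0.5, and 0.8 × 0.2 = 0.16 at p = 0.8. These powers are assumptions. The documents give none for labs, and they do not say that separate tests by arm will be run.

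**The case against.** The strongest reply is that the plan never says the lab comparison is within arm, or only within arm. Power and Sample Size Estimates speaks of pre-to-post change when it means a difference in change between two groups, so the lab phrase may be shorthand for a change score compared across arms. The introduction's talk of the intervention's effect, in a three-arm randomised trial, points the same way. This stands as far as it goes: a reader might infer that a within-arm result is prescribed, and the documents do not support that. But in the power section the words for the group comparison are present, as they are for the primary outcome, and for labs they are absent. A phrase that allows both readings prespecifies neither.

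A reader might also infer that glucose and insulin are drawn but are not outcomes. The assessment table contradicts this, and the list in Outcomes is introduced in a way that need not be exhaustive. What remains is a mismatch of lists. Nor is the month-18 draw excluded from analysis; its role is undefined.

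Three further points are fair. The introduction's times come from one sentence covering many measures, and the detailed schedules agree with each other. There is no lab entry criterion, so regression to the mean in the markers should not be leaned on. And the silence of Statistical Analysis is not peculiar to labs: it gives no arm comparison for zBMI, the self-regulation inventory or satisfaction either. That last point widens the gap; it does not excuse it for labs.

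**Conclusion.** The concern holds as under-specification of a secondary outcome. The only comparison stated for fasting labs is before versus after, with no arm contrast, model or time point, and on its plain reading it cannot deliver the effect of the intervention that the introduction promises. The reading as a before/after comparison is the natural one but not certain, and the conclusion does not depend on it, because the contrast and time point are open on either reading.

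The size is all 9 markers, at 2 follow-up times, without a stated contrast; one list that is 2 markers short of the other; and 2 introductory time points without a draw. No numerical bias can be given, since the documents contain no lab variability or power, and the 25% and 16% above are illustrative only. The primary analysis is not affected. The change should be made, because it uses data already scheduled and settles a choice that would otherwise be made after the results are known.

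**What to change.** In Outcomes, replace the lab phrase with text to this effect:

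- Each fasting marker is compared between AppCoach and Clinic, and between AppCoach and App, at month 6 and at month 18. The model is linear, with arm and the baseline value of that marker, on the log scale for skewed markers.
- Results are given as differences, or as ratios for logged markers, with 95% confidence intervals, and are labelled secondary without multiplicity control.
- Within-arm change is reported descriptively.

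Repeat the model in Statistical Analysis. Use one lab list in Outcomes, Research Blood Draws and the assessment table. In the introduction, give months 0, 6 and 18 for labs.

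The cost is wording only, with no new samples or visits. The downside is 36 secondary contrasts, with about 1.8 nominally significant by chance if nothing works. That is why they should be read as estimates with intervals, and why no single marker should be presented as confirmatory.

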Up to 404 adolescents (plus 1 parent/youth enrolled) will be recruited for the intervention arms and randomized 1:1:1 via stratified block randomization into one of the following groups: AppCoach, App or Clinic. Demographic information will be collected from all participants. During the intervention period the participants will not attend an inter-disciplinary in-clinic weight management intervention or any other medically supervised weight loss programs. If the participants have underlying comorbidities, they will continue to follow with routine subspecialty providers for standard of care of each underlying condition. Each participant's primary care provider, regardless of the method in which they were recruited (including those recruited from the greater LA county) upon request from participant, will receive a letter from the PI explaining that the individual will be participating in the research intervention during the allotted study period. Parental involvement is not required for those participants randomized to the AppCoach or App group; these participants will complete the intervention independently with the assistance of the coach (if applicable). Parental involvement is required for those participants randomized into the In-Clinic group. Upon completion of the intervention, if the participant was initially referred to a weight management clinic by their primary care provider, they will be offered continued enrollment in the inter-disciplinary weight management clinic for which they were initially referred. In order to further remove barriers to participation, all families who do not have a car will be offered free ridesharing transportation (UBER or Lyft) to- and from CHLA. Additionally, parking validation will be offered for families to park onsite at CHLA for research and/or intervention visits. To increase retention, participants are contacted once per month to maintain engagement. Research staff will provide families with dates of their scheduled assessments/visits. Participants are also given reminder phone calls the day before their assessment/visit.

Trial sites:

A participating trial site must fulfill the following eligibility criteria:

- 1) Have an independent weight management clinic that cares for adolescents.
- 2) The principal investigator and all the clinical research coordinators/staff at the site have been trained on, and understand, the study protocol.

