- 3) The site is within mobile phone range on the other hand, a trial site will be ineligible if it satisfies one or more of the following conditions:
 - 1) The principal investigator withdraws consent for participating in the study.
 - 2) The steering committee of the present trial judges the site to be inappropriate to recruit participants.

Initial trial sites include: CHLA, Los Angeles Biomedical Research Institute at Harbor-UCLA (LA Biomed), UCLA, and Cedars Sinai.

Site Training:

Each on-site CRC will receive 8 hours of training prior to recruitment start date.

Study Design:

404 reflect the 190 youth and 190 parent/guardians plus the 12 youth and 12 parent/guardian subjects that will be enrolled for the pilot study at CHLA.

We are aiming to recruit a total of 292 youth total with 1 parent/legal guardian per youth (total of 584 including the parent/guardian in the subject accrual number + 12 pilot youth + 12 pilot parent/guardian).

We plan to enroll 584 participants (youth & parent/guardian) into each intervention arm as follows:

[figure not shown]
CHLA/AltaMed = 404 (Pilot: 12 youth + 12 parent/guardians; Open enrollment: 190 youth & 190 parent/guardians)

UCLA = 60 (30 youth & 30 parent/guardians)

Harbor UCLA = 60 (30 youth & 30 parent/guardians)

Cedars Sinai = 60 (30 youth & 30 parent/guardians)

Pilot Group: We plan to initially recruit 12 patients from the CHLA EMPOWER clinic. The patients will be randomized to the three intervention arms and will complete a 2-month trial to assess intervention fidelity of the curriculum and identify any potential difficulties. The pilot subjects are reflected in the information above. .

Assessments:

Anthropometric Data

Height and weight will be assessed at in-person visits by study team member or self-reported if visit is conducted virtually via WebEx. Height will be measured using a Quick Medical stadiometer, accurate to 0.1 cm (Quick Medical, Issaquah, WA). Weight will be measured on a self-calibrating Mobile Stand Digital Scale,

accurate to 0.1 kg. Participants will wear minimal clothing during the height and weight measurements. BMI will be calculated as kilograms per square meter and BMI Z-score (zBMI) and percent over the 95th percentile (%BMI_{p95}) will be determined utilizing the CDC growth charts.

Physical Activity

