Twelve participants (and one of their parent/guardian) will be recruited from CHLA to complete a pilot intervention starting 2 months before the initial open recruitment commences. The youth participants will be randomized to one of the three arms and complete that intervention accordingly. The team members will continue to be monitored as they implement the intervention and barriers to execution will be evaluated. Those 12 participants will complete the full study period. If not protocol amendments are made they will be included in the final analysis, if protocol amendments are made they will be excluded.

Intervention Compensation:

Traditional payment: Payments will be provided at the end of study visits at months 3, 6, 12, and 18 as shown in the table below. Monthly payment: The participant may elect to receive compensation at monthly intervals for the first 6 months if desired. If this method is selected, the participant will provide the study team with their email address and a gift card will be emailed to them monthly based upon how much of the intervention they participate in or they can opt for the study team to email them images of the gift cards.

Each youth participant, regardless of which group they are assigned to, will receive compensation in the form of gift cards. Each youth participant has the opportunity to earn up to a total of \$200 for participation in this study. The amount of payment will be based upon how much intervention adherence occurs. The amount will be rounded to the nearest ten-dollar increment, by rounding up.

Parents/guardians will not be paid for their participation in this study.

For Group 1 (AppCoach) and 2 (App):

The app will automatically accrue points as the participant interacts with the app components. They will receive a pre-determined amount of points each time they open the app, each time they weigh in, each time they log a problem food, etc. The participants will be able to enter the motivation section of the app as desired to evaluate

how many points they have accrued. In addition, lack of participation with the app results in loss of points which will result in decreased financial gain. This balance is also available to the participants in real time. Points will be associated with financial quantity (1 point = 5 cents) and the youth participants will earn compensation as they complete the intervention as directed.

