This study will enroll 292 patients and equally allocate into 3 groups. All these calculations utilize an estimate of standard deviation of change based on the conservation of correlation of 0.5 between pre and post measurements within each group, based on Analysis of Variance (ANOVA) with two-sided Type I error of 5%. For the first study aim, the difference in the mean change of zBMI and %BMIp95 between baseline, 6 months, and 18 months across App+Coach, App, and Clinic, this study has at least 83% power to detect the effect size of 0.244 with the variance of the group means of 0.0003 for the mean change of zBMI and at least 89% power to detect the effect size of 0.263 with the variance of the group means of 2.903 for the mean change of %BMIp95. For the second study aim, the difference in zBMI and %BMIp95 mean change between App+Coach and Clinic, based on two sample t-test with two-sided Type I error of 5%, this study has 88% to detect an effect size of 0.580 corresponds to the mean difference of pre and post change in zBMI at least 0.040 standard deviation between the two groups and a 92% power to detect an effect size of 0.625 corresponds to the mean difference of pre and post change in %BMIp95 at least 4.08 percent between the two groups. For the third study aim, the difference in zBMI and %BMIp95 mean change between App+Coach and App, based on two sample t-test with two-sided Type I error of 5%, this study has 71% power to detect an effect size of 0.464 corresponds to the mean difference of pre and post change in zBMI at least 0.032 standard deviation between the two groups and a 68% power to detect an effect size of 0.452 corresponds to the mean difference of pre and post change in %BMIp95 at least 2.80 percent between the two comparison groups. Assuming 20% dropout rate, this study will achieve the desired study power of 80% for study aim 1 and 2. (nQuery + nTerim 4.0 and Stata/SE 15.1).

Statistical Analysis

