Statistical analysis: All statistical analyses were conducted in accordance with the planned study protocol.¹⁹ We estimated that 180 participants (60 in each group) would provide 89% power ($\alpha = 0.05$, 2 sided), to detect an effect size of 0.29 which corresponds to a difference of 4.0% %BMIp95 between the three groups. Analyses followed principles of intention-to-treat (ITT) and were performed in nQuery + nTerim 4.0 and Stata/SE 17 (StataCorp, College Station, TX). A two-sided significance level of 0.05 was utilized throughout the analyses. Our analysis approach is based under the assumption that data are missing at random, therefore, imputation using last observation was carried forward, and multiple imputation based on logistic regression model (for BEDS-7 scores only) were utilized to account for missing data. Results from the ITT analysis using imputation were compared as per protocol analysis with completed data. For all outcomes a per-protocol analysis was conducted for: full-program (completed full 24-week intervention period), pre-COVID (completed 24-week intervention prior to 3/15/2020), and during COVID (completed 24-week intervention after 3/16/2020). In addition, to account for impacts of the intervention dosage received on each primary outcome measure we conducted an analysis of participants who were adherent to at least 80% of the prescribed intervention modalities versus those who were nonadherence. Participants' demographic characteristics and baseline anthropometric measurements were reported as appropriately, mean and standard deviation or median and interquartile range for continuous variables, and frequency and percentages for categorical variables. The change in %BMIp95 between week 24 and baseline was assessed using analysis of variance (ANOVA) for all participants via ITT, per-protocol, PreCOVID and during COVID. First, the %BMIp95 was analysed in log scale mixed-effects linear regression model to assess the association between change in %BMIp95 and demographic characteristics (sex, ethnicity,

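### The six stated powers fit about 60 youth per arm (180 in total), not the stated enrolment of 292 or 292 less 20% dropout

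*Combined protocol and SAP*

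**What the plan says.** Power and Sample Size Estimates: "This study will enroll 292 patients and equally allocate into 3 groups". This is the only participant number in that section. Six powers follow, at a two-sided 5% level:

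- Aim 1 (three-group ANOVA): at least 83% at effect size 0.244 for zBMI, and at least 89% at 0.263 for %BMIp95.
- Aim 2 (AppCoach vs Clinic, t-test): 88% at 0.580 and 92% at 0.625.
- Aim 3 (AppCoach vs App, t-test): "this study has 71% power to detect an effect size of 0.464" for zBMI, and 68% at 0.452 for %BMIp95.

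The section closes: "Assuming 20% dropout rate, this study will achieve the desired study power of 80% for study aim 1 and 2". Aim 3 is not included.

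Statistical Analysis gives another basis: "We estimated that 180 participants (60 in each group) would provide 89% power", two-sided 0.05, "to detect an effect size of 0.29 which corresponds to a difference of 4.0% %BMIp95 between the three groups".

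The accrual text bears on the base for dropout. Study Design (the site accrual part) aims for 292 youth and describes a "total of 584 including the parent/guardian in the subject accrual number + 12 pilot youth + 12 pilot parent/guardian", which puts the pilot on top of 584. Its site list reaches 584 with the pilot already inside. Pilot Sessions says of the 12 pilot youth that "if protocol amendments are made they will be excluded". Enrollment and Retention says "Up to 404 adolescents (plus 1 parent/youth enrolled) will be recruited for the intervention arms".

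**The concern.** For a fixed effect size and test, power fixes the sample size. With about 97 youth per arm, an effect size of 0.580 should give power well above 88%, and 0.464 well above 71%. The printed figures look like those of a much smaller trial, and a number of that size, 180, appears in the next section without explanation.

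The reader therefore cannot tell which trial the power statements describe. The answer matters most for aim 3, which isolates the contribution of coaching; the background names this as a question the earlier pilot work could not answer. As printed, aim 3 looks knowingly underpowered. With 292 enrolled and 20% lost, it is close to 80%. If instead 180 were the number before dropout, the 80% statement would fail for one of the aim 1 endpoints.

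**Working it through.** **Inputs.** Effect sizes, powers, tests, alpha, 292 and 20% come from Power and Sample Size Estimates; 180, 89% and 0.29 come from Statistical Analysis.

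**Formulas.**
- t-test: noncentral t, two-sided 0.05, n = N/3 per arm (unrounded), df = 2n − 2, noncentrality d·√(n/2).
- ANOVA: noncentral F, 3 groups, df = 2 and N − 3, noncentrality N·f².

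**Step 1. Reproduce the plan's figures by solving each stated power for n.**

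| Comparison | Effect size | Stated power | n that gives it |
|---|---|---|---|
| Aim 1 zBMI | 0.244 | 83% | N = 177.2 |
| Aim 1 %BMIp95 | 0.263 | 89% | N = 180.2 |
| Aim 2 zBMI | 0.580 | 88% | 59.4 per arm |
| Aim 2 %BMIp95 | 0.625 | 92% | 59.0 per arm |
| Aim 3 zBMI | 0.464 | 71% | 59.7 per arm |
| Aim 3 %BMIp95 | 0.452 | 68% | 58.7 per arm |

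Six statements, from two tests and two endpoints, all point to about 60 per arm.

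**Step 2. Compute power (%) at each candidate N.**

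| N analysed | Aim 1 zBMI/%BMIp95 | Aim 2 | Aim 3 |
|---|---|---|---|
| Stated | 83/89 | 88/92 | 71/68 |
| 180 | 83.6/89.0 | 88.3/92.4 | 71.3/69.0 |
| 292 | 96.8/98.5 | 98.1/99.1 | 89.6/88.1 |
| 233 (292 × 0.8) | 92.2/95.6 | 94.9/97.2 | 81.9/79.9 |
| 243 (304 × 0.8: pilot added to 292 and analysed) | 93.3/96.3 | 95.6/97.7 | 83.5/81.6 |
| 224 (280 × 0.8: pilot inside 292 and excluded) | 91.1/94.8 | 94.1/96.7 | 80.4/78.3 |
| 144 (180 × 0.8, hypothetical) | 73.9/80.5 | 80.3/85.8 | 61.4/59.2 |

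Only 180 matches. Against 233, aim 2 is understated by 94.9 − 88 = 6.9 and 97.2 − 92 = 5.2 points, and aim 3 by 81.9 − 71 = 10.9 and 79.9 − 68 = 11.9 points.

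**Step 3. Check the stated mean differences.** Aims 2 and 3 put AppCoach 4.08 from Clinic and 2.80 from App on %BMIp95, so App lies 4.08 − 2.80 = 1.28 from Clinic. The variance of (0, 1.28, 4.08), divisor 3, is 2.903, as stated. For zBMI, (0, 0.008, 0.040) gives 0.0003, as stated. The mean differences are consistent across aims.

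**Step 4. Find what aim 3 needs for 80%.** It needs 73.9 per arm for zBMI and 77.8 for %BMIp95. Unrounded, 292 × 0.8 / 3 = 77.9, so %BMIp95 sits on the line and how the pilot is counted decides the side.

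**Step 5. Test the Statistical Analysis set.** At f = 0.29, three groups and N = 180, power is 94.2%, not 89%. Power of 89% at f = 0.29 needs N of about 149. At N = 180, 89% corresponds to f = 0.263, the %BMIp95 effect size in the power section. The implied SD there is √2.903 / 0.263 = 6.48. With that SD, a 4.0-point difference gives f = 4.0 × (√2/3) / 6.48 = 0.291 if the other two arms are equal, and 4.0 / √6 / 6.48 = 0.252 if the arms are evenly spaced. So 0.29 and 4.0 can go together, but only under a pattern of means that is not stated.

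**Step 6. Check the counts.** Sites: 404 + 60 + 60 + 60 = 584 = 2 × 292. Youth: 190 + 12 + 30 + 30 + 30 = 292, pilot included. If 180 is the evaluable number, 20% dropout implies 180 / 0.8 = 225 enrolled; 292 enrolled would imply 1 − 180/292 = 38% lost.

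**The case against.** The strongest reply is that no harm follows. At 292, before or after 20% dropout, every power exceeds the printed one. The aim 1 powers are worded as lower bounds and so remain true, as does the 80% sentence for aims 1 and 2. All of that stands. It does not cover aims 2 and 3, whose powers are point figures.

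Second, the section never states the n per arm behind its powers, so 180 may be the evaluable number, in which case all six are right. That is possible, but no text says so, and the stated 20% dropout does not connect 180 with 292.

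Third, the inputs are not perfectly consistent. The SDs implied for %BMIp95 change are 4.08/0.625 = 6.53, 2.80/0.452 = 6.19 and 6.48; for zBMI they are 0.040/0.580 = 0.069 and √0.0003/0.244 = 0.071. This is a fair qualification of Step 3. The sample-size conclusion rests on the stated effect sizes and powers, so it does not depend on these SDs.

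Fourth, the 89% in Statistical Analysis can be approached by adding something unstated: 20% lost from 180 gives 87.9%. That section states 60 per group and no dropout, so this part is a query about which figure is wrong and is less firm than the main point.

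Finally, the 79.9% for aim 3 comes from rounding down to 233; unrounded it is 80.0%. The pilot moves aim 3 by only about 2 points either way, and whether the pilot is excluded depends on amendments.

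**Conclusion.** The point holds. The six powers describe about 180 youth, not 292 and not 292 less 20%, and no text reconciles the two numbers. If 292 with 20% dropout is right, the plan understates aim 2 by 5 to 7 points and aim 3 by 11 to 12 points, and wrongly presents aim 3 as well short of 80% when it is borderline: about 82% for zBMI and 80% for %BMIp95, with a range of 80.4% to 83.5% and 78.3% to 81.6% depending on the pilot. If 180 is the evaluable number, the powers stand and the enrolment figure is unexplained. Only if 180 is the number before dropout does the 80% statement fail, for aim 1 zBMI at 73.9%. Separately, 180, 89% and 0.29 do not agree as stated.

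These results assume equal arms, the tests and alpha the plan states, and its effect sizes taken as given. The matter should be fixed; it does not threaten the design.

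**What to change.** 1. State one youth enrolment target and one evaluable number, and say whether the 12 pilot youth count in each. Bring Study Design and Pilot Sessions into line with this.
2. Restate all six powers at the evaluable number, with the n per arm:
   - 292 enrolled, 20% dropout, about 233 evaluable: aim 1 92%/96%, aim 2 95%/97%, aim 3 82%/80%.
   - Pilot inside 292 and excluded, about 224 evaluable: 91%/95%, 94%/97%, 80%/78%.
   - In both cases, describe aim 3 as borderline for %BMIp95.
3. If 180 was intended, say whether it is before or after dropout. If after, the printed powers stand and enrolment at 20% dropout is 225. If before, withdraw the 80% statement for aim 1 zBMI.
4. In Statistical Analysis, recheck 180, 89% and 0.29 against each other and state the pattern of means behind 0.29.
5. Minor: in Enrollment and Retention, replace 404 adolescents with the youth target. Study Design shows that 404 counts CHLA youth and parents together (190 + 190 + 12 + 12).

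The cost is text edits in five sections. No extra participants are needed, and neither the design nor the analysis changes.
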